23.6. Study Binders

Investigator Binders will be provided by the Sponsor to be maintained by the designated investigational center staff. Each binder will have tabs to facilitate filing of study documents. Examples include:

- Medtronic Contact Information
- CV's & Medical Licenses
- Agreement(s)
- Delegation of Authority Log
- Training Records
- Subject Screening/Enrollment Logs
- Randomization Documentation (if applicable)
- Laboratory Documentation
- Case Report Forms (CRFs) & Instructions
- Sponsor/Monitor Visit Log
- Investigator Brochure
- Protocol and Amendments
- Device Instructions for Use (IFU)
- IRB/EC Documentation & Approvals
- IRB/EC Approved Consent Documents
- IRB/EC approved Investigator's Brochure/ Report of Priors
- Regulatory Authority approval or notification
- Financial Disclosures
- Insurance certificates (EMEA only)
- Reports
- Essential Correspondence
- Product Accountability
- Regulations and Guidance Documents
- Site Study Materials

- Subject Study Materials
- Note to File
- Miscellaneous
- Relevant communication

There will be an individual file for each subject which will include, but will not be limited to:

- Source Documents
- Signed and dated Informed Consents
- Adverse Event Notifications, if any
- Questionnaires
- Study Logs, if any

For EMEA only: The investigator will clearly mark the clinical records to indicate that the subject is enrolled in this clinical study.

For EMEA only: Where copies of the original source document as well as printouts of original electronic source documents are retained, these shall be signed and dated by a member of the investigation site team with a statement that it is a true reproduction of the original source document.

23.7. Monitoring Plan

Monitoring will be conducted to ensure the protection and safety of human subjects, the quality and integrity of the clinical data, and compliance with the protocol. The Monitoring Plan will give details on how and when data review will be conducted by clinical monitors. It will be updated and revised as needed due to changes in documents or processes.

Employees of the Sponsor, or its designees, who have received appropriate training, will serve as the Study Monitor(s). Monitoring visits will be conducted based on Medtronic's Standard Operating Procedures and the needs of the study. Quality documents will be followed for the conduct of all activities related to monitoring for this study.

Site Qualification and Initiation Visits will be completed prior to enrollment of the first subject. On Site study monitoring activities will include an inspection of completed study documents, source document verification and reporting, verification of database accuracy and completeness. All subjects enrolled in the trial will be monitored and the eCRF data verified against the subjects' source documents. Following each monitoring visit, a report will be prepared and submitted to the Sponsor. From initiation of study to close out visit, the Study Monitor(s) will assume primary responsibility for communications between the Study Investigators and the Sponsor.

The Principal Investigator is responsible for ensuring that investigational center staff is appropriately trained to manage the protocol. Initial and ongoing investigational center training will be provided during the Site Initiation Visit, subsequent monitoring visits, and regular investigational center contact. All investigational center staff must complete and sign the Study Training Record(s) and maintain the record(s) in the investigational center regulatory binder. Prior to enrollment of the first subject, Investigators and study coordinators who will be participating in enrollment, eCRF completion, device insertion/application, device training, and consenting subjects must complete the Sponsor-required training. Investigators and staff who are actively engaged in the study after the start of subject enrollment must complete all required training before their involvement starts.

All monitoring visits and visits from the Sponsor to the investigational center will be recorded using the Monitoring Visit Log. The log will be kept in the investigational center regulatory binder and the original will be collected and submitted to the sponsor.

23.8. Publication Policy

The contents of this protocol, the manuals pertaining to this study and the results of the investigation are confidential and may not be published or disclosed without the written consent of Medtronic Diabetes. The identity of the subjects may not be disclosed, unless required by law, to any persons not immediately involved in the study or the study procedures. The results of the clinical study will be submitted for publication.

24. Statistical Methods and Data Analysis

DURING HOME PERIOD:

24.1. Descriptive Endpoints

- The mean change in A1C will be presented from baseline to end of study
- Change of Total Daily Dose (TDD) of insulin from baseline to end of study
- Change of weight from baseline to end of study
- Time spent in Auto Mode versus time spent in Manual Mode
- Time in different range (% of SG): SG < 50, 54, 60, 70 mg/dL, 70 mg/dL ≤ SG ≤ 180 mg/dL, SG > 180, 250 mg/dL, 350 mg/dL
- Number of Events, AUC and Time in the hyperglycemic range: sensor glucose (SG) > 180, 250, 350 mg/dL
- Number of Events, AUC and Time in the hypoglycemic range: SG < 50, 54, 60, and 70 mg/dL

24.2. Safety Data Summarized

- Serious Adverse Events (SAE), Serious Adverse Device Effects (SADE)
- Unanticipated Adverse Device Effects (UADE)
- Incidence of Severe Hypoglycemia
- Incidence of DKA

DURING HOTEL STUDY

During the Run-In Period

Low Management Suspend before Low Evaluation:

- Success rate of prevention of hypoglycemia (i.e. 1 - percent of *Low Management Suspend before Low* experiments that have 2 or more consecutive reference glucose values of ≤ 65 mg/dL)
- *Low Management Suspend before Low* Performance
- Sensor performance

During the Hotel Period in the Study Period

Auto Mode Evaluation:

- Time in different range (% of i-STAT): BG < 50, 54, 60, 70 mg/dL, 70 mg/dL ≤ BG ≤ 180 mg/dL, BG > 180, 250 mg/dL
- Number of Events, AUC and Time in the hyperglycemic range: i-STAT® glucose > 180, 250, 350 mg/dL

- Number of Events, AUC and Time in the hypoglycemic range: i-STAT® glucose < 50, 54, 60, and 70 mg/dL

24.3. Exploratory Analysis

24.3.1. Analysis of Primary Endpoint

The primary effectiveness endpoint is change in A1C from baseline to end of 3-month treatment period, defined as A1C measured at the 3-month treatment visit minus A1C measured at the randomization visit. The goal is to show simple superiority in reducing A1C from baseline to end of 3-month study period.

24.3.2. Analysis of Secondary Endpoint

The secondary endpoints are hierarchically ordered and will be evaluated in the fixed sequence from endpoint 1 to 3 during the study phase.

- **Secondary Endpoint: % of Time in Euglycemia (70 – 180 mg/dL)**

The overall mean change in % of time in euglycemia (70-180 mg/dL) from baseline to the end of study will be estimated and compared by a simple superiority paired test and a significance level of 0.025 (one-sided).

- **Secondary Endpoint: % of Time in Hyperglycemia (> 180 mg/dL)**

The overall mean change in % of time in hyperglycemia (> 180 mg/dL) from baseline to the end of study will be estimated and compared by a simple superiority paired test and a significance level of 0.025 (one-sided).

- **Secondary Endpoint: % of Time in Hypoglycemia (< 70 mg/dL)**

The overall mean change in % time in hypoglycemia (< 70 mg/dL) from baseline to the end of study will be estimated and compared by a simple superiority paired test and a significance level of 0.025 (one-sided).

24.3.3. Sample Size Justification

24.3.3.1. Sample Size for Primary Endpoint

The overall mean change in A1C from baseline to the end of study will be estimated and compared by a simple superiority paired test and a significance level of 0.025 (one-sided).

The hypothesis is mathematically expressed as:

Ho: $\mu \geq 0\%$

Ha: $\mu < 0\%$

Where μ is the mean of % of change in A1C (3-month - baseline). The null hypothesis will be rejected if the one-sided 97.5% upper confidence limit of the mean change in A1C is less than 0%.

Assuming the mean of change in A1C from baseline to the 3-month follow-up visit is zero, the standard deviation of change in A1C is 1.1%, SAS power and sample size calculator shows that a total of 80 subjects (7-13 years old) will provide 90% power to detect the difference of 0.4% and with one-sided type I error of 0.025.

A minimum of 95 subjects will be enrolled to account for subject attrition

24.3.3.2. Sample Size for Secondary Endpoint: % of Time in Euglycemia (70 – 180 mg/dL)

The overall mean change in % of time in euglycemia (70-180 mg/dL) from baseline to the end of study will be estimated and compared by a simple superiority paired test and a significance level of 0.025 (one-sided).

Ho: $\mu \leq 0\%$

Ha: $\mu > 0\%$

Where μ is the mean of change in % of time in euglycemia (3-month - baseline). The null hypothesis will be rejected if the one-sided 97.5% lower confidence limit of the mean change in % of time in euglycemia is greater than 0%.

Assuming the mean of change in time in euglycemia (%) from baseline to the 3-month follow-up visit is zero, the standard deviation of change in percentage time in euglycemia is 11.0%, SAS power and sample size calculator shows that a total of 80 subjects (7-13 years old) will provide 90% power to detect the difference of 4.0% and with one-sided type I error of 0.025.

A minimum of 95 subjects will be enrolled to account for subject attrition

24.3.3.3. Sample Size for Secondary Endpoint: % of Time in Hyperglycemia (> 180 mg/dL)

The overall mean change in % of time in hyperglycemia (> 180 mg/dL) from baseline to the end of study will be estimated and compared by a simple superiority paired test and a significance level of 0.025 (one-sided).

The hypothesis is mathematically expressed as:

Ho: $\mu \geq 0\%$

Ha: $\mu < 0\%$

Where μ is the mean of change in % of time in hyperglycemia (3-month - baseline). The null hypothesis will be rejected if the one-sided 97.5% upper confidence limit of the mean change in % of time in hyperglycemia is less than 0%.

Assuming the mean of change in time in hyperglycemia (%) from baseline to the 3-month follow-up visit is zero, the standard deviation of change in percentage time in hyperglycemia is 11.0%, SAS power and sample size

calculator shows that a total of 80 subjects (7-13 years old) will provide 90% power to detect the difference of 4% and with one-sided type I error of 0.025.

A minimum of 95 subjects will be enrolled to account for subject attrition

24.3.3.4. **Sample Size for Secondary Endpoint: % of Time in Hypoglycemia (< 70 mg/dL)**

The overall mean change in % time in hypoglycemia (< 70 mg/dL) from baseline to the end of study will be estimated and compared by a simple superiority paired test and a significance level of 0.025 (one-sided).

The hypothesis is mathematically expressed as:

Ho: $\mu \geq 0\%$

Ha: $\mu < 0\%$

Where μ is the mean of change in % of time in hypoglycemia (3-month - baseline). The null hypothesis will be rejected if the one-sided 97.5% upper confidence limit of the mean change in % of time in hypoglycemia is less than 0%.

Assuming the mean of change in time in hypoglycemia from baseline to the 3-month follow-up visit is zero, the standard deviation of change in percentage time in hypoglycemia is 4.0%, SAS power and sample size calculator shows that a total of 80 subjects (7-13 years old) will provide 90% power to detect the difference of 1.5% and with one-sided type I error of 0.025.

A minimum of 95 subjects will be enrolled to account for subject attrition

24.4. **Coding of Adverse Events**

Adverse events will be coded based on the latest version of the Medical Dictionary for Regulatory Activities (MedDRA) thesaurus.

24.5. **Subject Feedback**

Descriptive summary will be used to characterize data from questionnaires that are given to subjects to record feedback,

24.6. **Interim Analysis**

After 1200 patient days an interim report will be generated.

24.7. **Final Reports**

24.7.1. **Study Phase Final Report for Subjects 7-13 Years Old**

A study phase final report will be generated once the 7-13 year old cohort have completed the study period. Descriptive and exploratory endpoints and safety data for 7-13 years old subjects will be summarized and presented in the final report.

24.7.2. **Study Phase Final Report for Subjects 2-13 Years Old**

An addendum study phase final report will be generated once the 2-6 year old cohort have completed the study period. Descriptive and exploratory endpoints and safety data for 2-13 years old subjects will be summarized and presented in the final report.

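### The 90% power stated for the hypoglycemia endpoint is a single-test figure; under the protocol's own fixed sequence it is about 80% at n=80 for the effects it powers for

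*Protocol*

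**What the plan says.** Section 24.3.2 of the protocol sets the testing procedure: "The secondary endpoints are hierarchically ordered and will be evaluated in the fixed sequence from endpoint 1 to 3 during the study phase". The listed order is time in 70-180 mg/dL (euglycemia), time above 180 mg/dL (hyperglycemia) and time below 70 mg/dL (hypoglycemia). Each is a paired superiority test at one-sided 0.025.

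Sections 24.3.3.2 to 24.3.3.4 then justify the sample size one endpoint at a time:

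- Euglycemia: "the standard deviation of change in percentage time in euglycemia is 11.0"%, and "80 subjects (7-13 years old) will provide 90% power to detect the difference of 4.0"%.
- Hyperglycemia: "the standard deviation of change in percentage time in hyperglycemia is 11.0"%, and "80 subjects (7-13 years old) will provide 90% power to detect the difference of 4% and" one-sided type I error 0.025.
- Hypoglycemia: "the standard deviation of change in percentage time in hypoglycemia is 4.0"%, and "80 subjects (7-13 years old) will provide 90% power to detect the difference of 1.5"%.

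Each section adds that at least 95 subjects will be enrolled to allow for attrition. None mentions the sequence. Section 24.1 defines the middle range with both limits included ("70 mg/dL ≤ SG ≤ 180 mg/dL, SG > 180"), so the ranges below 70, 70-180 and above 180 mg/dL count every sensor reading exactly once.

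**The concern.** In a fixed sequence, the hypoglycemia hypothesis can be rejected only if the euglycemia and hyperglycemia hypotheses have already been rejected. The power of the third step is therefore the probability that all three tests succeed. That cannot exceed the power of the third test alone and is usually lower. A reader who takes the 90% in 24.3.3.4 together with the procedure in 24.3.2 would expect a 90% chance of showing a hypoglycemia reduction, if the stated effects are true.

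There is also a structural point. Because the three ranges partition sensor time, the three mean changes must sum to zero. The stated differences, +4.0, -4 and -1.5, sum to -1.5. They are legitimate as three separate detectable differences, but they cannot serve as one scenario for the sequence. The protocol therefore gives three powers that do not describe the same trial, and none for the procedure it prescribes. What is at stake is the accuracy of a stated power, not the safety conclusion of the study.

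**Working it through.** **Inputs (protocol 24.3.2 and 24.3.3.2-24.3.3.4).** n = 80; one-sided alpha 0.025; SDs of change 11, 11 and 4 percentage points; differences 4, 4 and 1.5.

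**1. The protocol's own figures.** For a paired t-test with n - 1 = 79 degrees of freedom, the critical value is 1.990 and the noncentrality is (difference/SD) × √80.

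- Euglycemia and hyperglycemia: (4/11) × 8.944 = 3.252, power 89.5% (90.2% by the normal approximation).
- Hypoglycemia: (1.5/4) × 8.944 = 3.354, power 91.2% (91.8% by the normal approximation).

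The stated 90% is reproduced for each test taken alone.

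**2. Correlation between the tests.** If the three changes sum to zero within each subject, the SDs fix the covariances:

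- cov(eu, hyper) = (4² - 11² - 11²)/2 = (16 - 121 - 121)/2 = -113, so r = -113/121 = -0.93.
- cov(eu, hypo) = cov(hyper, hypo) = (121 - 121 - 16)/2 = -8, so r = -8/44 = -0.18.

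No correlation has to be brought in from outside.

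**3. Which mean changes are possible.** A zero-sum set with hyperglycemia at -4 or lower and hypoglycemia at -1.5 or lower needs euglycemia at +5.5 or higher. So +5.5/-4/-1.5 is the smallest set that meets all three stated magnitudes. Keeping euglycemia at +4 and hypoglycemia at -1.5 leaves hyperglycemia at -2.5. Keeping both 4-point differences leaves hypoglycemia at 0.

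**4. Power in sequence at n = 80.** Simulated paired t-tests with the covariances above, at least 200,000 trials per case:

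| Changes (70-180 / >180 / <70) | Pass step 1 | Pass steps 1-2 | Pass steps 1-3 |
|---|---|---|---|
| +4 / -4 / -1.5 (as stated; not zero-sum, reference only) | 89.5% | 87% | 79.5% |
| +5.5 / -4 / -1.5 | 99% | 90% | 81% |
| +6 / -4.5 / -1.5 | >99% | 95% | 86% |
| +7 / -5.5 / -1.5 | >99% | 99% | 90.5% |
| +8 / -6.5 / -1.5 | >99% | >99% | 91% |
| +4 / -2.5 / -1.5 | 89.5% | 52% | 46% |
| +4 / -4 / 0 | 89% | 87% | 2% |

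In the last row the hypoglycemia null is true, so 2% is a type I error rate, not power. In the +4/-2.5/-1.5 row the hyperglycemia test alone has only 52% power: (2.5/11) × 8.944 = 2.033. Most of the loss there comes from an effect below the 4 points powered for, not from the sequence.

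**5. More subjects.** For +5.5/-4/-1.5, third-step power is 89% at n = 95 and 91% at n = 100. For +4/-2.5/-1.5 it is 56% and 58%. An n of 95 requires every subject in the minimum enrolment to be evaluable. An n of 100 would follow from the 120-completer target in section 5 if about 20 completers are aged 2-6. That split is an assumption, since 20 is the minimum enrolled in that age group.

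**The case against.** The strongest reply is that no sentence in 24.3.3 is false. Each 90% stands under its own endpoint heading, with its own hypotheses and SD, and is right in that setting. The protocol nowhere claims 90% for the sequence, nor offers +4/-4/-1.5 as a joint scenario. Detail on sequential power may sit in an SAP that is not shown. This stands as far as the arithmetic goes: a reader might infer a miscalculation, and there is none. It does not remove the mismatch, because the protocol itself states both the sequence and a power for its last step.

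Second, a reader might infer that true power for hypoglycemia is as low as 46%, or that it can never exceed 81%. Neither is supported. The 46% needs a hyperglycemia effect of 2.5 points, below the design value. The 81% is no ceiling: a detectable difference is not a forecast, and with larger euglycemia and hyperglycemia effects the third step approaches its single-test 91% at n=80.

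Third, 80 is the lowest planning number, and a moderately larger evaluable cohort restores about 90% at +5.5/-4/-1.5. That is fair, but the protocol attaches its 90% to 80 subjects.

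Fourth, the consequence is small. Section 24.3 labels these tests exploratory and the study purpose is safety. The success criteria in 11.4.7 and the stopping rules in section 19 do not use the tests, and the A1C endpoint arrives at the same n=80. All of this stands.

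**Conclusion.** The concern holds in this limited form. The 90% figures are valid as single-test powers only. Under the prescribed sequence, the chance of passing the hypoglycemia test at n=80 is about 80% at the effects the protocol powers for: 79.5% at the stated differences and 81% at the smallest zero-sum set that meets them. The shortfall is about 10 points. For euglycemia, tested first, the 90% also holds within the sequence, unless the A1C test is meant to gate the secondary endpoints, which the text does not say.

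The result rests on approximately normal changes, the protocol's SDs, a true 1.5-point hypoglycemia reduction, and all three percentages being computed on the same readings. The joint sets other than the stated differences are illustrations built from the zero-sum identity, because the protocol gives none. Nothing here shows that the trial is too small for its purpose. The point is worth correcting because the correction is cheap, but its impact is modest.

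**What to change.** In 24.3.3.2, 24.3.3.3 and 24.3.3.4, describe each 90% as single-test power. Then add to 24.3.3 a statement such as:

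> The secondary endpoints are tested in the fixed sequence of 24.3.2. With mean changes of +5.5, -4 and -1.5 percentage points in 70-180, >180 and <70 mg/dL (sum zero), the power to pass steps 1, 2 and 3 is about 99%, 90% and 81% at n=80, and about 89% for step 3 at n=95.

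If the sponsor expects different changes, the same calculation should be given for its own zero-sum set, at n=80 and at the expected number of evaluable subjects aged 7-13.

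The cost is a few sentences and one short simulation. The stated power for an exploratory endpoint becomes less favourable; the design, the sample size and the number of children enrolled do not change.

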24.7.3. Continued Access Phase Final Report for Subjects 2-13 Years Old

An addendum continuation phase final report will be generated once the 2-13 year old cohort have completed the continuation phase visits. Safety data will be summarized and presented in the final report

25. Human Factors

25.1. Electronic Diary

Use-related problems related to Auto Mode can only be experienced by subjects after run in period.

During the run-in period, starting at Visit 2, when subjects receive device training, they will be instructed to call the Medtronic 24-Hour HL to report technical problems (referenced in study protocol and EZ reference guide). In addition, all subjects and their parent(s)/guardian(s) will be asked to complete an electronic diary that captures use-related difficulty (see definition below) with the 670G insulin pump, e.g. issues that were resolved without help from the Medtronic 24-Hour HL, but nevertheless presented subjects with a challenge in terms of general understanding of the device.

Subjects and their parent(s)/guardian(s) will be instructed to complete an electronic diary entry as soon as possible after the time the difficulty occurred. The electronic diary online address will be provided to subjects. As part of the EZ reference guide given to all subject (see Investigator Site binder for details regarding subject training materials), the following brief explanation of use-related difficulty will be provided

Use-related difficulty is any scenario or situation in which you had trouble completing a task and you believe the device was the source of the issue. For instance:

- The pump did not perform as expected or as you were trained
- The task took more steps than you thought necessary
- You were frustrated with the pump when you performed the task
- The screens and/or controls on the pump were confusing

The following questions will appear on the electronic diary page:

1. Did the use-related difficulty involve the Medtronic study device (Y/N)?
2. Please describe the use-related difficulty you experienced (open-ended)?
3. What were you attempting to do when you experienced the difficulty (open-ended)?
4. What did you expect to happen and what actually did happen (open-ended)?
5. If the device did not seem to operate as you expected, were you using it in an unusual condition (e.g. extreme heat, cold, humidity)? (Y/N)
 - a. If the answer to question 5 is "Yes": Please describe what actually you were doing at the time (open-ended)
6. Did you receive an alarm (Y/N)?

- a. If yes, please describe the alarm.
7. Did you have to refer to the user guide or training material (Y/N)?
 - a. If yes, please describe the alarm.
8. Did you encounter any unexpected or unanticipated situations when the pump did not perform as expected (Y/N)?
 - a. If the answer to question 8 is “yes”: Please describe the situation and what you expected to happen (open-ended)
9. Was the difficulty overly burdensome (Y/N)?

The Human Factors Engineer (HFE) assigned to the study will retrieve the survey forms and review the answers provided to the above set of questions. The HFE will work with the Clinical Study team to make sure that none of the forms contain information about potential safety issues that would require intervention by any of the investigators. All use-related data from the diaries and from Help Line reports will be used to inform the system design, the user guide and/or relevant training materials.

